
treatment does not occur on the randomization day for these subjects, it must occur within 4 weeks after signing the informed consent form (ICF).

The TI must re-confirm that the treatment goal has been aligned with the subject before performing treatment at the Initial Treatment visit. The trained TI will administer treatment to enhance the volume and aesthetic appearance of nose with VOLUMA with Lidocaine to subjects randomized to the treatment group. The allowed study injection sites are the nasal dorsum, columella and anterior nasal spine. Non-midline areas of the nose, nasal tip, and glabella area are not allowed for injection. VOLUMA with Lidocaine must be injected into upper-periosteal (supraperiosteal and/or supraperichondrial) layer following a specified injection technique to obtain optimal nose aesthetic improvement with minimal safety concern. Following treatment, the TI will document treatment characteristics, including injection volume, injection site, and injection plane. The TI will also use an 11-point scale to assess the ease of injection (ie, 0 = difficult, 10 = easy) and the product moldability (ie, 0 = stiff, 10 = moldable), separately. Subjects will assess the procedural pain on an 11-point scale (ie, 0 = no pain, 10 = worst pain imaginable) immediately after receiving treatment. The TI must observe the subject for any acute adverse events (AEs), such as vascular embolism, for at least 30 minutes after completing treatment.

The treatment group subjects may undergo a touch-up injection 8 (+1) weeks after initial treatment if both the subject and TI assess that the optimal aesthetic improvement goal of the nose was not achieved. Urine pregnancy testing must be confirmed as negative before treatment. If a touch-up treatment is performed, the TI will document treatment characteristics, assess the ease of injection, and the product moldability. Subjects will assess the procedural pain immediately after treatment. The TI must monitor the subject for any acute AEs, such as vascular embolism, for 30 minutes after treatment.

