4.1 Structure

This is a prospective, multicenter, randomized, no-treatment-controlled study. Up to 9 investigational sites will enroll and follow subjects who meet the study criteria.

This trial consists of 2 periods including a Control Period and a Post-control Period. The Control Period is the period from the randomization visit until the primary endpoint visit (24 weeks after the last treatment for the treatment group or randomization for the control group). The main purpose of the Control Period is to compare the primary effectiveness parameter, the volume change of nose area basing on 3D imaging data, between the treatment group and the control group. During the Control Period, subjects randomized to the treatment group will receive treatment and be followed for evaluation of safety and effectiveness. During this period, subjects randomized to the control group will not receive treatment but will be followed for safety and effectiveness evaluations.

The Post-control Period is the period after the primary endpoint visit until the end of the study visit (48 weeks after the last treatment for the treatment group or 24 weeks after the last treatment for the control group). The main purpose of Post-control Period is to collect long-term safety and effectiveness data for the treatment group subjects, and to collect safety and effectiveness data for control group subjects who received treatment. Safety and effectiveness data from the treated control group subjects will be analyzed separately.

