During the visit scheduled 8 weeks after initial treatment, before conducting any scheduled actions, the TI must confirm whether the subject needs touch-up treatment after evaluating the initial treatment outcome and getting the subject's agreement. If a touch-up treatment is agreed on, then the Touch-up Treatment Visit and all scheduled procedures will be conducted, if the decision is not to conduct touch-up treatment, then the Week 8 Visit and all scheduled procedures will be conducted. Urine pregnancy testing must be conducted and confirmed as negative before performing touch-up treatment.

For treatment group subjects, routine follow-up visits for safety and effectiveness will occur at Weeks 8, 16, and 24 (primary timepoint) after the last treatment. 3D digital images will be collected, and the 5-point Global Aesthetic Improvement Scale (GAIS) will be assessed separately by the EI (judged live) and the subject (using a mirror) by comparing with pre-treatment (baseline) photos. In addition, the subject (using a mirror) will assess satisfaction with the treatment outcome using the 5-point Nose Satisfaction Scale (NSS) and the subject's willingness to recommend the treatment to a friend. Vital signs will be collected at all visits, and laboratory sample collection for routine hematology, chemistry and urinalysis will be performed at Week 24. The procedures to be performed during the control period are specified in [Table 2](#).

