5.1. General Considerations

- The primary analysis will be performed after the database is locked and randomization schedule is released.
- Participants will receive treatment at the outset of the study (treatment group) or have treatment delayed until Week 24 (control group). The delayed treatment for control group is optional and referred to as "Optional Treatment".
- Control Period (CP), Treated Period (TP) are defined in Table 5-1.

Table 5-1 **CP and TP definition**

| Randomization | Period | Treatment | Start Date | End Date |
|---------------|--------|------------------------|---------------------------------|---|
| Group | | Group Label | | |
| Treatment | СР | VOLUMA | Initial treatment date | The date of effective assessment for Week 24. If multiple assessments fall into Week 24 window, the date of the assessment included in the Week 24 analysis will be used as end date. For participants who exit before Week 24, the end date is study exit date. For participants with intermittent missing assessment at Week 24, the target day for Week 24 (Day 169) will be the end day. |
| | TP | VOLUMA | Initial treatment date | Study exit date |
| Control | СР | Control | Randomization date | For participants who do not receive optional treatment If multiple assessments fall into Week 24 window, the date of the assessment included in the Week 24 analysis will be used as end date. For participants who exit before Week 24, the end date is study exit date. For participants with intermittent missing assessment at Week 24, the target day for Week 24 (Day 169) will be the end day. For participants who receive optional treatment: The day before optional treatment |
| | ТР | VOLUMA Post-Control | Optional initial treatment date | Study exit date |

JUVÉDERM® VOLUMA® with Lidocaine

- For CP, effectiveness analyses and baseline characteristics will be performed on the mITT population using the "as-randomized" assignment. One of the sensitivity analyses for the primary endpoint will be based on PP population. Safety analyses for CP will be conducted using the Safety Population based on "as-treated" assignment.
- For TP, effectiveness and safety summaries will be performed on the VITP and VOTP using "as-treated" assignment.
- For applicable effectiveness endpoints, baseline is defined as the last non-missing value prior to the start of study treatment for treatment group or no later than randomization date for control group.

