5.6.3. Adverse Events

An AE will be considered a TEAE if the AE began or worsened (increased in severity or became serious) on or after the date (and time, if known) of the initial treatment for treatment group and after randomization for control group.

An AE will be considered a TESAE if it is a TEAE that additionally meets any SAE criterion.

TEAEs will be summarized by treatment group for CP using the Safety population.

TEAEs will also be summarized for TP using VITP and VOTP, respectively.

The number and percentage of participants with TEAEs as well as the events in the following AE categories will be summarized for the above populations as described in Table 5-7.

If more than 1 AE is coded to the same preferred term for the same participant, the participant will be counted only once for that preferred term using the most severe and most related occurrence for the summarizations by severity and by relationship to study intervention.

Listings of all TEAEs, TESAEs, TEAEs leading to discontinuation, and death will be presented.

Table 5-7 TEAE Summaries

| Endpoint | Description | Timing | Methodology |
|--------------------------------|--|--------|--|
| Overall summary | Overall summary only for the following categories: TEAEs Treatment-related TEAEs Treatment-related TEAEs at injection site Treatment-related TEAEs not at injection site TESAEs Treatment-related TESAEs Treatment-related TESAEs Treatment-related TESAEs at injection site Treatment-related TESAEs not at injection site Discontinued due to TEAE Deaths | CP, TP | Categorical descriptives, event descriptives |
| TEAEs | Overall summary and by SOC and PT Overall summary and by SOC, PT, and maximum severity | CP, TP | Categorical descriptives, event descriptives |
| Treatment-related TEAEs | Overall summary and by SOC and PT Overall summary and by SOC, PT, and maximum severity Overall summary by maximum severity, time to onset, duration, action taken and outcome | CP, TP | Categorical descriptives, event descriptives |
| TESAEs | Overall summary and by SOC and PT | CP, TP | Categorical descriptives, event descriptives |
| AEs leading to discontinuation | Overall summary and by SOC and PT | CP, TP | Categorical descriptives, event descriptives |

SAP 1894-701-008 amendment 1

5.6.4. **Injection Site Response**

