6.4. Data Handling Convention

6.4.1. Analysis Window

6.4.1.1. Effectiveness

Most recent treatment refers to initial treatment if touch-up is not performed, otherwise touch-up treatment. The reference day is defined for each group and each study period. The analysis visit windows for effectiveness endpoints are defined in Table 6-1 for the treatment group and in Table 6-2 and Table 6-3 for the control group. If more than 1 measurement exist in one visit, the measurement that close to the target date of the visit will be used for summary analysis. If both measurements have the same time interval to the target date, the later one will be used for summary analysis. But all measurements will be listed in data listings

If analysis date ≥ reference date, then
Analysis day = analysis date – reference date + 1

If analysis date < reference date, then
Analysis day = analysis date - reference date

JUVÉDERM® VOLUMA® with Lidocaine

Table 6-3 Effectiveness Analysis Visit Definitions for Treatment Group during Control Period and Treated Period

| Scheduled Visit | Target Day of the Visit | Analysis Visit Window |
|-----------------------|----------------------------|---------------------------|
| Most Recent Treatment | Day 1 | Day 1 |
| Week 8 | Day 57 | Days [2, 85] |
| Week 16 | Day 113 | Days [86, 141] |
| Week 24 | Day 169 | Days [142, 211] |
| Week 36 | Day 253 | Days [212, 295] |
| Week 48 | Day 337 | Day 296 to study exit day |

Table 6-4 Effectiveness Analysis Visit Definitions for Control Group during Control Period

| Scheduled Visit | Target Day of the Visit | Analysis Visit Window |
|-------------------|----------------------------|---|
| Randomization Day | Day 1 | Day 1 |
| Week 8 | Day 57 | Days [2, 85] |
| Week 16 | Day 113 | Days [86, 141] |
| Week 24 | Day 169 | Day 142 to study exit day if the participant does not receive optional treatment, or to the day of treatment if the participant receives optional treatment |

Table 6-5 Effectiveness Analysis Visit Definitions for Control Group during Treated Period

| Scheduled Visit | Target Day of the Visit | Analysis Visit Window |
|---------------------------------|----------------------------|---------------------------|
| Most Recent Treatment | Day 1 | Day 1 |
| Week 8 Post-optional treatment | Day 57 | Days [2, 85] |
| Week 16 Post-optional treatment | Day 113 | Days [86, 141] |
| Week 24 Post-optional treatment | Day 169 | Day 142 to study exit day |

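### The Control Period TEAE table compares crude percentages over unequal at-risk periods: 24 to 33 weeks for VOLUMA, 24 to 25.3 weeks for control

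*SAP*

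**What the plan says.** SAP 5.6.3: "TEAEs will be summarized by treatment group for CP using the Safety population". Table 5-7 gives categorical and event descriptives for this period. An event counts as treatment-emergent from the initial treatment in the VOLUMA group and from randomization in the control group.

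SAP 5.1, Table 5-1, starts the VOLUMA Control Period at the initial treatment date and ends it at "The date of effective assessment for Week 24". The clock for that visit is set in SAP 6.4.1.1: "Most recent treatment refers to initial treatment if touch-up is not performed, otherwise touch-up treatment". The protocol agrees. In section 6.2.2.2, "routine follow-up visits for safety and effectiveness will occur at Weeks 8, 16, and 24 (primary timepoint) after the last treatment", and section 4.1 defines the primary endpoint visit as "24 weeks after the last treatment for the treatment group or randomization for the control group". According to the synopsis, treatment group subjects "may undergo a touch-up injection 8 (+1) weeks after initial treatment".

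For controls, Table 5-1 runs the period from randomization to the Week 24 assessment. If optional treatment is taken, the period ends the day before it. Protocol 6.2.3.2 allows that treatment up to 10 days after the Week 24 visit.

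The protocol's safety population (8.1) holds treated subjects only. SAP Table 4-1 adds untreated controls with at least one follow-up assessment, and this is what makes the Control Period table a between-group display. The other TEAE summaries, for the Treated Period, use VITP and VOTP and have no untreated comparator. SAP 5.6.1, on extent of exposure, covers injected volume and sites, not time at risk.

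**The concern.** A crude percentage of participants with an event rises with the time they are watched. If one group is observed longer, intercurrent illnesses and other events unrelated to the device accumulate there, and the table shows an excess even when the underlying rates are the same.

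SAP 1.1 lists TEAEs as a primary safety variable. In the visible SAP the Control Period table is the only place where TEAEs in VOLUMA participants stand beside those of concurrent untreated participants. The size of the artefact also depends on how many participants have a touch-up. Protocol 4.3.4 leaves that largely to the judgement of the subject and the treating investigator, so it cannot be known in advance.

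**Working it through.** **The plan's own figures.** The protocol synopsis gives the Control Period as up to 8 weeks of treatment plus 24 weeks of follow-up for the treatment group, 8 + 24 = 32 weeks, against 24 weeks for control. The SAP definitions reproduce this asymmetry. The plan's one power figure concerns nose volume; no sample size or power is stated for safety.

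**At-risk time by group**
- VOLUMA without touch-up: 24 weeks.
- VOLUMA with touch-up at 8 (+1) weeks: 24 + 8 = 32 to 24 + 9 = 33 weeks.
- Control: 24 weeks, or at most 24 weeks + 9 days = 24 + 9/7 = 25.3 weeks (optional treatment by day 10, period ending the day before).

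These take visits on their target days. The Week 24 analysis window for VOLUMA extends to Day 211 after the last treatment (SAP Table 6-3), so individual periods can be longer.

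With touch-up share *s*, mean VOLUMA time is 24 + 8*s* to 24 + 9*s* weeks. At *s* = 25% this is 26.0 to 26.25 weeks, 1.08 to 1.09 times 24. At *s* = 100% it is 32 to 33 weeks, 1.33 to 1.38 times 24.

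**Spurious excess with no true difference.** Assume the same constant hazard in both groups and a 24-week incidence *p*. Incidence over *T* weeks is then 1 − (1 − *p*)^(*T*/24). For *p* = 30%:
- *T* = 32: 1 − 0.70^(32/24) = 37.8%
- *T* = 33: 1 − 0.70^(33/24) = 38.8%
- *T* = 25.3: 1 − 0.70^(25.3/24) = 31.3%

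The VOLUMA percentage is (1 − *s*) × *p* + *s* × (touched-up incidence). Example with *s* = 50% and *T* = 32: 0.5 × 30.0 + 0.5 × 37.8 = 33.9%. The excess is 3.9 points against controls at 24 weeks (30.0%) and 2.6 points against controls at 25.3 weeks (31.3%).

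Neither *s* nor *p* is in the documents, so both are varied. In each cell the lower figure takes touch-up at 8 weeks and controls at 25.3 weeks; the upper takes touch-up at 9 weeks and controls at 24 weeks. Units are percentage points, VOLUMA minus control.

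| Touch-up share | *p* = 10% | *p* = 20% | *p* = 30% |
|---|---|---|---|
| 0% | −0.5 to 0 | −1.0 to 0 | −1.3 to 0 |
| 25% | 0.3 to 0.9 | 0.5 to 1.6 | 0.6 to 2.2 |
| 50% | 1.0 to 1.7 | 1.9 to 3.2 | 2.6 to 4.4 |
| 75% | 1.8 to 2.6 | 3.4 to 4.8 | 4.6 to 6.6 |
| 100% | 2.6 to 3.5 | 4.8 to 6.4 | 6.5 to 8.8 |

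If events are counted only on Days 1 to 169 in both groups, *T* is the same and the excess is zero under equal hazards.

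**Check on a person-time rate.** Suppose 30% of participants have an event half a week after injection and none occur later. Per 100 participants, time to first event or end of period is 30 × 0.5 + 70 × 24 = 1,695 weeks over 24 weeks, and 30 × 0.5 + 70 × 32 = 2,255 weeks over 32 weeks. The rates are 30/1,695 = 1.77 and 30/2,255 = 1.33 per 100 participant-weeks. The same harm looks about 25% smaller over the longer period.

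**The case against.** The strongest reply is that the safety analysis is descriptive. SAP 1.1 and Table 5-7 give no test, confidence interval or risk difference, and there is no safety hypothesis. The period lengths are published in the protocol. The artefact concerns background events, while Table 5-7 reports treatment-related TEAEs separately and ISRs are summarized per injection from a 56-day diary. The main device-safety outputs therefore do not depend on how long the untreated group is followed. The bias also mostly works against the product, so it is unlikely to hide harm.

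Most of this stands, and it limits the point to interpretation. It does not remove it. Relationship to treatment is judged by the treating investigator (protocol 11.1.8), who is not blinded (4.3.3). The all-TEAE comparison with untreated participants is the one that does not rest on that judgement. Publishing the period definitions also does not tell the reader the actual mean duration, because the touch-up share is unknown.

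Three stronger readings are tempting but unsupported:
- A reader might infer that the comparison cannot be read at all. It can be read with the durations beside it; what cannot be done is to attribute the whole difference to the device.
- A reader might infer that this is the only concurrent safety comparison. That can be said only of TEAEs in the visible text. SAP 5.6.6 and 5.6.7 are not shown, and the table specifications are in a separate document.
- A reader might infer that person-time rates should replace the crude table. Protocol section 11 names bruising, swelling, redness and tenderness at the treatment site as expected events. Where such reactions cluster after injection, the calculation above shows how a rate can dilute them. Events caused by a touch-up are also a real effect of the regimen, not an artefact.

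**Conclusion.** The point holds as a limited one. By the SAP's own definitions the Control Period TEAE table sets 24 to 33 weeks of VOLUMA follow-up beside 24 to 25.3 weeks of control follow-up, with no adjustment in the visible text. No error rate or decision rule is touched.

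The false excess in background TEAEs is about 0.3 to 3.5 points at a 10% 24-week incidence and about 0.6 to 9 points at 30%, for touch-up shares of 25% to 100%. With no touch-ups it is zero or up to 1.3 points in the other direction at 30%. These figures rest on equal constant hazards, visits on target days, and incidences and touch-up shares that are assumed, not documented. A single figure from the top of the range would overstate what can be known: it needs a high background incidence, a high touch-up share and controls stopping at exactly 24 weeks.

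**What to change.** In SAP 5.6.3 and Table 5-7, keep the crude Control Period table as the full record and add:

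1. Control Period duration by group.
2. A supplementary same-length TEAE summary, counting only events with onset on Days 1 to 169 from initial treatment (VOLUMA) or randomization (control), and stopping for a control at the day before optional treatment if that comes first.

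An exposure-adjusted incidence by group may be added as a further supplement, with a note that it assumes a roughly constant hazard and can dilute events that cluster after injection. The all-TEAE comparison between groups should be read alongside the same-length table, which does not replace the crude one.

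The cost is SAP wording and one or two tables from dates already collected; no study procedure changes. The downside is that the same-length table leaves touched-up participants only 24 − 9 = 15 to 24 − 8 = 16 weeks after the second injection. Later post-touch-up events are missing from it but remain in the crude Control Period and Treated Period tables.

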Injection site responses (ISR) must be recorded by subjects daily for 56-days in a diary starting from the day of treatment (initial treatment and touch-up treatment, if performed). If an ISR is ongoing at the end of the 56-day post-treatment subject diary after the last treatment (ongoing ISR from initial treatment will be recorded in the touch-up 56-day post-treatment subject diary, if performed), the TI (or designee) will follow the outcome of the ongoing ISR and will document the entire course of the ISR. Safety phone calls will occur 3 days after treatment (initial and touch-up, if performed).

For treatment group subjects, routine follow-up visits for safety and effectiveness will occur at Weeks 8, 16, and 24 after the last treatment. 3D imaging and the 5-point Global Aesthetic Improvement Scale (GAIS) assessed separately by the Evaluating Investigator (EI) and subjects, will be performed at all 3 visits. At Weeks 8, 16 and 24, several effectiveness evaluations will be conducted including: the subject assessment of satisfaction with the treatment outcome using the 5-point Nose Satisfaction Scale (NSS) and subject's willingness to recommend the treatment to a friend. Laboratory sample collection for routine hematology, chemistry, and urinalysis will be performed at Week 24 and vital signs (ie, blood pressure at sitting position, pulse, respiratory rate, temperature) will be collected at all on-site visits.

Control Group Subjects: Post-randomization, Treatment and Follow-up

Control group subjects will undergo routine follow-up visits for safety and effectiveness, including 3D imaging and EI assessment of the GAIS, at Weeks 8, 16, and 24.

Post-control Period

Treatment Group Subjects: Post-randomization, Treatment(s) and Follow-up

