6.2.2.3 Post-randomization, Treatment(s) and Follow-up – Control Group

The control group subjects will undergo 3D imaging and EI assessment of the GAIS at Weeks 8, 16, and 24. The procedures to be performed during the control period are specified in [Table 3](#).

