11.1 Definitions

11.1.1 Adverse Event

An AE is defined in accordance with ISO 14155 as “any untoward medical occurrence, unintended disease or injury, or untoward clinical signs (including abnormal laboratory findings) in subjects, users, or other persons, whether or not related to the investigational medical device.” This definition includes events related to the investigational medical device or comparator and events related to the procedures involved except for events in users or other persons, which only include events related to investigational medical devices.

Disease signs and symptoms that existed prior to the study treatment are not considered AEs unless the condition recurs after the subject has recovered from the pre-existing condition or the condition worsens in intensity or frequency during the study.

AEs will be monitored throughout the study beginning with signing the ICF. At each post-baseline visit, the investigator will begin querying for AEs by asking each subject a general, non-directed question such as “Have you had any changes to your condition since your last visit?” Previous AEs and changes in therapy/concomitant medications are to be updated. Directed questioning and examination will then be done as appropriate. All reportable AEs and clinically significant abnormal laboratory findings will be documented on the appropriate eCRF.

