12.7 Testing of Biological Specimens

At screening and at month 6 posttreatment, blood samples will be collected and prepared for routine hematology and chemistry testing by a central laboratory located in China.

Routine hematology tests including:

- levels of hemoglobin and hematocrit, concentration of red blood cells, mean cell volume, mean cell hemoglobin, mean cell hemoglobin concentration, red blood cell morphology, and the concentration of white blood cells, neutrophils (% absolute), lymphocytes (% absolute), monocytes (% absolute), eosinophils (% absolute), basophils (% absolute), and platelets

Chemistry tests including:

- hepatic function tests: total bilirubin, direct bilirubin, alkaline phosphatase, alanine aminotransferase, aspartate aminotransferase, gamma-glutamyl transpeptidase, total protein, and albumin
- renal function tests: urea nitrogen, creatinine, uric acid, calcium, and phosphorous
- others: lactate dehydrogenase, glucose, triglycerides, cholesterol, and creatinine kinase

At screening and at month 6 posttreatment, urine samples will be collected for routine macro and micro panel of tests conducted by the central laboratory in China to assess color and clarity, specific gravity, pH, and concentration of protein, glucose, ketones, bilirubin, urobilinogen, blood, nitrite, and leukocyte esterase, and for microscopic analysis.

At screening, on treatment days prior to injection, and at study exit, a trained research staff member at each investigational site will perform pregnancy testing on urine samples from women of childbearing potential. The urine pregnancy test employed will test for the presence of human chorionic gonadotropin and should have a sensitivity of at least 50 mIU/mL.

All blood and urine samples (ie, not including samples for urine pregnancy testing) will be stored at the central laboratory for the duration of the study. The central laboratory will be responsible for sample destruction when the study sites have been closed. Allergan shall have full ownership rights to any biological specimens/samples derived from the study.

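### The Control Period TEAE comparison rests on unequal scheduled laboratory testing: the visible text gives the VOLUMA arm a Week 24 panel and untreated controls none

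*SAP*

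**What the plan says.** **VOLUMA arm.** Protocol 6.2.2.2 describes visits at Weeks 8, 16 and 24 after the last treatment and adds: "Vital signs will be collected at all visits, and laboratory sample collection for routine hematology, chemistry and urinalysis will be performed at Week 24". The Synopsis (Control Period, treatment group) agrees.

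**Control arm.** Protocol 6.2.2.3 says "The control group subjects will undergo 3D imaging and EI assessment of the GAIS at Weeks 8, 16, and 24" and refers to Table 3 for the procedures. The Synopsis says "Control group subjects will undergo routine follow-up visits for safety and effectiveness, including 3D imaging and EI assessment of the GAIS". Neither names a laboratory sample. The Synopsis account of the Post-control Period places the control group's laboratory samples at Week 24 after their last treatment. Protocol 12.7 gives the general rule: "At screening and at month 6 posttreatment, blood samples will be collected and prepared for routine hematology and chemistry testing". It times urinalysis in the same way.

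**What counts as an AE.** The definition in Protocol 11.1.1 includes abnormal laboratory findings. On recording it says: "All reportable AEs and clinically significant abnormal laboratory findings will be documented on the appropriate eCRF".

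**The analysis.** SAP 5.6.3 says "TEAEs will be summarized by treatment group for CP using the Safety population". SAP Table 4-1 puts untreated participants with at least one follow-up assessment in that population. SAP Table 5-1 ends the VOLUMA arm's Control Period on the date of the Week 24 assessment. It ends a control's Control Period no later than the day before any optional treatment. Table 5-7 lists overall, SOC, preferred-term, severity and relatedness summaries. None of them separates or footnotes events found by a scheduled laboratory sample.

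**The concern.** The Control Period TEAE table is the only concurrent comparison of harm between injected and untreated participants. Such a comparison is fair only if both arms are looked at equally hard. On the visible text, one arm has a scheduled blood and urine panel at the end of the period and the other has none. Clinically significant abnormalities that cause no symptoms would then be found by schedule in the VOLUMA arm, and in controls only if someone happened to test.

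The table is descriptive, but readers will compare its columns. A few laboratory terms appearing only under VOLUMA could come from testing or from the device, and the table as planned gives no means of telling which. The overall TEAE row would carry the same excess without showing it.

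**Working it through.** **1. The plan's own figure.** There is none to reproduce: neither document gives an AE rate. The only inputs from the plan are the arm sizes, 120 and 40 (SAP Section 3).

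**2. Scheduled panels, from the text.**

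| | Screening | Control Period, after screening | After optional treatment |
|---|---|---|---|
| VOLUMA arm | yes | Week 24 after last treatment | not applicable |
| Control arm | yes | none named | Week 24 after last treatment, if treated |

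Planned Control Period panels are therefore up to 120 × 1 = 120 against 40 × 0 = 0. This reading rests on more than the silence of Protocol 6.2.2.3. Section 12.7 ties sampling to month 6 after treatment, a time point that an untreated control does not have. The Synopsis separates control GAIS ratings, timed from randomization, from control laboratory samples, timed from the last treatment. Under Protocol 6.2.3.2 a control who declines optional treatment has completed the study and, on this text, never has a second panel.

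**3. Do the panel events fall inside the Control Period?** The panel belongs to the visit whose date ends the VOLUMA Control Period. An AE with onset dated to sampling is inside. One dated to a later central-laboratory result is generally outside. The SAP text available gives no rule; SAP 6.4.2.1 deals only with missing or partial dates.

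**4. Size, by assumption.** Let b be the risk of any other TEAE, equal in both arms, and q the risk that a panel yields a recorded AE. Assume that the two are independent, that every VOLUMA participant is sampled, that onset is dated to sampling, and that the device has no effect. Then

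- VOLUMA rate = 1 − (1 − b)(1 − q)
- control rate = b
- artificial excess = q(1 − b)

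For b = 20% and q = 5%: 1 − 0.80 × 0.95 = 24.0% against 20.0%, an excess of 4.0 points. Other values:

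| q | Excess, b = 10% | Excess, b = 20% | Excess, b = 40% | Expected VOLUMA panel AEs (120q) | Control panel AEs if tested alike (40q) |
|---|---|---|---|---|---|
| 1% | 0.9 | 0.8 | 0.6 | 1.2 | 0.4 |
| 2% | 1.8 | 1.6 | 1.2 | 2.4 | 0.8 |
| 5% | 4.5 | 4.0 | 3.0 | 6 | 2 |
| 10% | 9.0 | 8.0 | 6.0 | 12 | 4 |

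Excesses are in percentage points. Under the plan the scheduled-panel count for controls is 0 in every row, not 40q.

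**5. Effect of the fix.** In a row that leaves out panel-only events, both arms have rate b under the same assumptions, so the artificial difference is b − b = 0.

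**The case against.** The strongest objection is that the governing schedule cannot be seen. Protocol 6.2.2.3 defers to Table 3, which is not in the text reviewed. The schedules that the SAP cites as Tables 1-1 to 1-3 are not there either. The SAP text also passes from 5.6.5 to 5.6.8, so a laboratory analysis may sit in between; Protocol 8.3.4 does promise laboratory summaries. The prose for controls is not exhaustive: the Synopsis uses the word including, and 6.2.2.3 omits AE questioning, which 11.1.1 requires at every post-baseline visit. All of this stands, and it is why the first step is to check Table 3. It does not cancel the positive evidence in the Synopsis and in Section 12.7, nor the fact that SAP 5.6.3 and Table 5-7, which are visible, define the TEAE table without any separation.

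A reader might infer that controls cannot show a laboratory AE at all. The documents do not support that. The Synopsis and Protocol 7.5 have AEs monitored in both groups from consent to exit, so an off-schedule, clinically significant finding in a control is an AE. The difference lies in scheduled testing.

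It is also fair to say that the effect may be slight. Only clinically significant findings are recorded, in healthy adults. The table carries no test or decision rule, and SOC and preferred-term rows plus a listing let a careful reader spot laboratory terms. Injection-related AEs would raise b in the VOLUMA arm and reduce the excess q(1 − b). These points limit the importance of the matter. They do not make the overall row like for like.

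Finally, taking recorded AEs out of the main safety table could hide a real device effect. That is a good reason to add a row and remove nothing.

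**Conclusion.** The concern holds as a matter of unequal scheduled ascertainment. On the visible text, the VOLUMA arm has one post-screening panel in the Control Period and untreated controls have none, while SAP 5.6.3 sets their TEAEs side by side without separation or comment. The size is unknown and probably small. The range of 0.6 to 9 points rests wholly on assumed rates (q from 1% to 10%, b from 10% to 40%) and on onset being dated on or before the Week 24 assessment date.

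A reader might go further and conclude that any VOLUMA excess in laboratory terms would be an artefact of testing. That does not follow: the plan leaves artefact and device effect indistinguishable, which is the reason for adding a like-for-like comparison. Nor can it be said that the plan certainly omits a control panel while Table 3 is unseen.

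**What to change.** 1. Check protocol Table 3 for a control-group laboratory panel during the Control Period.
2. If there is none, keep every TEAE in the main Control Period table. Add to SAP Table 5-7 one between-arm row of Control Period TEAEs that leaves out events identified only from the protocol-scheduled Week 24 sample. Show those panel-only events in a separate VOLUMA row, and footnote that controls had no scheduled Control Period panel.
3. State in SAP 5.6.3 that the onset of a panel-detected AE is the sampling date.
4. Leave the Treated Period tables for VITP and VOTP as they are.
5. If Table 3 does schedule a control panel, reconcile it with the Synopsis, Protocol 6.2.2.3 and Protocol 12.7. The extra rows are then not needed.

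The cost is a short SAP change, one flag on laboratory-detected AEs, two table rows and a footnote. No visit or sample is added and no safety data are lost. The drawback is some case review to decide which AEs were found only through the scheduled sample.
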